6.0 DRUG INFORMATION

See the consent document for toxicities. All other information is available on the COG website in the commercial agent monographs manual titled “Drug Information for Commercial Agents used by the Children’s Oncology Group.” On the COG website, this manual is provided under Standard Sections for Protocols

at: https://www.cogmembers.org/site/pages/default.aspx?page=Prot_reference_materials

Please see [Appendix IV](#) for drug interactions associated with the drugs used in this study.

7.0 EVALUATIONS/MATERIAL AND DATA TO BE ACCESSIONED

Timing of protocol therapy administration, response assessment studies, and surgical interventions are based on schedules derived from the experimental design or on established standards of care. Minor unavoidable departures (up to 72 hours) from protocol directed therapy and/or disease evaluations (and up to 1 week for surgery) for valid clinical, patient and family logistical, or facility, procedure and/or anesthesia scheduling issues are acceptable (except where explicitly prohibited within the protocol).

7.1 Clinical Evaluation of RQ-PCR

Patients on AAML1331 require bone marrow samples for RQ-PCR of PML-RAR α testing for clinical reasons. These specimens must be sent to one of the approved labs for PML-RAR α RQ-PCR testing and the cost is not covered by the study. It should be billed as a regular clinical lab through the institution/insurance/patient as appropriate. A list of approved labs is available on the protocol-specific web page of the COG website located at <https://cogmembers.org/PROT/AAML1331/AAML1331ValidatedRQ-PCRLabsList.pdf>

7.1.2 Required Specimens

Site should always confirm with the selected RQ-PCR laboratory with regard to what quantity of specimen and tube is appropriate for testing at their lab.

In general specimens can be drawn as follows:

- 3 mL of bone marrow in a purple top.

7.2 End of Therapy & Follow-up

STUDIES TO BE OBTAINED	End of Therapy	Follow-Up	Relapse
History			X
Physical Exam with VS	X	Monthly to 12 months, q3 months to 36 months, q6 months to 48 months, then yearly to 10 years	X
Ht, Wt, BSA			X
Performance Status	X		X
CBC, differential, platelets	X	Monthly to 12 months, q3 months to 36 months, q6 months to 48 months then yearly to 10 years	X
Electrolytes (Ca ⁺⁺ , Mg ⁺⁺ , K ⁺), and Creatinine			X
Uric Acid			X
Echocardiogram or MUGA, and ECG	X	Yearly to 10 years	
BMA for morphology			X
BMA for flow cytometry, cytogenetics & FISH			X
BMA for clinical RQ-PCR of PML-RAR α	X	Strongly recommended for all patients with high risk APL and those patients with standard	X

		
risk APL who required the MRD positive Consolidation Cycle: q3 months until 3 years from diagnosis.
	
--	--	--	--

See COG Late Effects Guidelines for recommended post treatment follow-up at:
<http://www-survivorshipguidelines.org/>

Note: Follow-up data are expected to be submitted per the Case Report Forms (CRFs) schedule.

7.3 Research Studies for which Patient Participation is Optional

Optional Study	Specimen	Diagnosis	Day 1	Day 8	Day 15	Day 29	Consolidation Cycle 1 Day 1	Consolidation Cycle 2 Day 43	Consolidation Cycle 3 Day 1	End of therapy	2 years post therapy	4 years post therapy	Relapse (either molecular or morphologic)
FLT3	Bone Marrow	X ^{1,3}						X					X
MRD	Bone Marrow AND Peripheral Blood	X ¹				X		X		X			X
Coagulopathy	Peripheral Blood in Citrate tube AND Peripheral Blood in CTI tube	X ²	X	X	X	X							
Neurocognitive Testing ⁴	CogState						X		X	X	X	X	
	BRIEF						X		X	X	X	X	
	Psychologist administered battery									X	X	X	

¹ If bone marrow is not obtained at diagnosis, may submit peripheral blood only.

² Requested if available.

³ Diagnostic specimens collected on Project Every Child (APEC14B1).

⁴ See [Section 16.4.1](#) for evaluation time point details.

8.0 CRITERIA FOR REMOVAL FROM PROTOCOL THERAPY AND OFF STUDY CRITERIA

8.1 Criteria for Removal from Protocol Therapy

- a) Failure to achieve an hCR/hCRi by Day 70 of Induction.
- b) Refractory CNS leukemia following 6 doses of intrathecal therapy.
- c) Failure to achieve molecular remission following the MRD Positive Consolidation cycle (mitoxantrone/cytarabine/ATRA)
- d) Relapse (hematologic, molecular or extramedullary) during Consolidation therapy.
- e) Repeat eligibility studies (if required) prior to initiation of protocol therapy are outside the parameters required for eligibility (see [Section 3.2](#)).
- f) Refusal of further protocol therapy by patient/parent/guardian.
- g) Completion of planned therapy.
- h) Unacceptable toxicity due to protocol therapy (see [Section 5.0](#))
- i) Physician determines it is in patient's best interest.
- j) Development of a second malignancy.
- k) Pregnancy

Patients who are off protocol therapy are to be followed until they meet the criteria for Off Study (see below). Follow-up data will be required unless patient is taken Off Study.

8.2 Off Study Criteria

- a) Death.
- b) Lost to follow-up.
- c) Patient enrollment onto another COG study with tumor therapeutic intent (e.g., at recurrence).
- d) Withdrawal of consent for any further data submission.
- e) Tenth anniversary of the date the patient was enrolled on this study.
- f) RQ-PCR determines patient to be PML-RAR α negative at diagnosis or RQ-PCR inevaluable (including patients determined to have a variant RARA translocation such as PLZF-RAR α , NPM1-RAR α , NUMA-RAR α).
- g) RQ-PCR sample not collected prior to initiation of protocol therapy.

9.0 STATISTICAL CONSIDERATIONS

9.1 Statistical Design

This is a non-randomized study of pediatric patients with APL stratified by risk group based on presenting WBC. Patients with standard risk disease (WBC < 10,000/ μ L at diagnosis) and high risk disease (WBC \geq 10,000/ μ L at diagnosis) will be assessed independently for outcome measures. The primary endpoint will be event-free survival (EFS). EFS is defined as the time from on study to failure to achieve hematological CR prior to start of Consolidation, persistence of molecular positive disease after MRD Positive Consolidation course (mitoxantrone/cytarabine/ATRA chemotherapy course following Consolidation Cycle 2), relapse (molecular, morphologic or extramedullary), or death.

Other outcome measures will include the hematological, molecular, and cytogenetic remission rates after each phase of therapy, early death rates, overall survival from on study, treatment related mortality, relapse risk, percentage of patients experiencing Grade 3 or higher toxicity or any grade of cardiac toxicity, time to count recovery, and duration of hospitalization.

When AAML1331 was developed and opened, outcome data from the most recent prior COG APL study AAML0631 was not mature. Thus, similar to AAML0631, the statistical plan of AAML1331 initially used the historical comparator AIDA 0493 (the most mature and best outcomes published for pediatric APL). During the course of AAML1331 accrual, AAML0631 outcome data became available and demonstrated that the addition of arsenic trioxide (ATO) consolidation therapy resulted in higher survival estimates compared to AIDA0493. Therefore the statistical plan of AAML1331 was amended to include a primary outcome comparison to AAML0631.

AAML0631 included 2 cycles of ATO consolidation and has excellent survival results. Thus, we would not expect AAML1331 to be significantly superior to AAML0631, but rather the goal of the study should be to show non-inferiority to AAML0631. This design is clinically appropriate because the AAML1331 treatment regimen represents a significant reduction in cytotoxic chemotherapy treatments which should result in decreased toxicities (both in the short and long term). To demonstrate that AAML1331 therapy is non-inferior to AAML0631 would be a major step forward in reducing treatment morbidity and mortality.

Standard risk APL treatment on AAML0631 included 335 mg/m² of doxorubicin equivalents whereas AAML1331 includes no anthracycline for standard risk APL patients. Historical data suggests that patients with >300 mg/m² of anthracycline have a cardiomyopathy odds ratio of 27 compared to patients not exposed to anthracycline.⁷¹ A large cohort of children treated with anthracycline and with long term follow-up has showed a clinical heart failure rate of 9.8% at 20 years when the cumulative anthracycline dose was >300 mg/m². Among patients who developed clinical heart failure (and did not die from their malignancy) the rate of death due to their heart failure was approximately 40%.⁷² Therefore we believe it is appropriate to consider powering our analysis of standard risk APL outcomes on AAML1331 in a comparison that allows a very modest decrease in EFS from the 97% observed on AAML0631.

Our non-inferiority (NI) margin of 10% for the standard risk APL comparison is designed to allow sufficient power (80%) to demonstrate non-inferiority for an observed EFS of 95%. This allows a modest decrease of 2% from the 97% EFS observed on AAML0631 to account for the benefit of elimination of anthracycline chemotherapy (also knowing that most APL relapses are successfully treated with further therapy and autologous transplant consolidation). We also feel that the NI margin for the high risk group is clinically relevant given the degree of uncertainty in the AAML0631 survival estimates. The high risk group includes a NI margin of 14.5%, but the AAML0631 24 month EFS estimate has a similarly large confidence interval of +/-13%.

9.2 Patient Accrual and Expected Duration of Trial

The Children's Oncology Group recently completed a Phase III study of children with newly diagnosed APL (COG AAML0631). On AAML0631, the actual accrual rate was 31.5 patients per year (20 standard risk, 11.5 high risk). Allowing for up to 5% of patients

to be ineligible for study enrollment, enrollment of up to 158 patients will be required to assure that a total of 96 eligible patients with standard risk APL and 54 eligible patients with high risk APL are enrolled. It is estimated that accrual goals will be met in 5 years for both standard and high risk APL.

9.3 Statistical Analysis Methods

9.3.1 Analysis Plan

Primary Objective 1

EFS for patients with SR APL on this study will be compared against a fixed EFS of 97% at 24 months, which was observed for patients with SR APL treated on AAML0631.

The non-inferiority null hypothesis is that the 2-year EFS for SR patients on this study is not non-inferior to 97% with a non-inferiority (NI) margin of 10%. The alternative hypothesis is that the 2-year EFS for SR patients is non-inferior to 97% with a NI margin of 10%. The Kaplan-Meier method will be used to estimate 2-year EFS along with 90% log-minus-log transformed confidence limits for SR patients. If the lower confidence limit for the 2 year EFS exceeds $97\% - 10\% = 87\%$, non-inferiority will be concluded. The final analysis of EFS will occur after a minimum of 2-years following the enrollment of the last eligible SR patient.

Primary Objective 2

EFS for patients with HR APL on this study will be compared against a fixed EFS of 83% at 24 months, which was observed for patients with HR APL treated on AAML0631. The non-inferiority null hypothesis is that the 2-year EFS for HR patients on this study is not non-inferior to 83% with a NI margin of 14.5%. The alternative hypothesis is that the 2-year EFS for HR patients is non-inferior to 83% with a NI margin of 14.5%. The Kaplan-Meier method will be used to estimate 2-year EFS along with 90% log-minus-log transformed confidence limits for SR patients. If the lower confidence limit for the 3-year EFS exceeds $83\% - 14.5\% = 68.5\%$, non-inferiority will be concluded. The final analysis of EFS will occur after a minimum of 2 years following the enrollment of the last eligible HR patient.

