9.3.2 Power Calculations

Primary Objective 1

A study of 96 evaluable SR patients using a one-sided type I error rate of 0.05 and 10% NI margin will have 80%, 91% and 97% power to reject the null hypothesis that the 2-year EFS is not non-inferior to 97% for a 2-year EFS of 95%, 96% and 97% respectively. Power calculations were performed using PASS 14.

Primary Objective 2

A study of 54 evaluable HR patients using a one-sided type I error rate of 0.05 and 14.5% NI margin will have 80% power to reject the null hypothesis that the 2-year EFS is not non-inferior to 83% for a 2-year EFS of 83%. Power calculations were performed using PASS 14.

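### The high-risk non-inferiority rule tests the 3-year EFS limit, but its threshold, hypotheses, power and follow-up are all set for 2-year EFS

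*Combined protocol and SAP*

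**What the plan says.** Section 9.3.1, Primary Objective 2, opens at two years: "EFS for patients with HR APL on this study will be compared against a fixed EFS of 83% at 24 months". The null hypothesis is that "the 2-year EFS for HR patients on this study is not non-inferior to 83" per cent with the 14.5-point margin, and the alternative is framed the same way: "The alternative hypothesis is that the 2-year EFS for HR patients is non-inferior to 83% with a NI margin of 14.5" per cent. The estimator is also at two years, "The Kaplan-Meier method will be used to estimate 2-year EFS along with 90% log-minus-log transformed confidence limits", although that sentence goes on to name standard-risk patients under the high-risk objective. Timing follows suit: "The final analysis of EFS will occur after a minimum of 2 years following the enrollment of the last eligible HR patient".

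The decision sentence alone changes the time point: "If the lower confidence limit for the 3-year EFS exceeds" 83% − 14.5% = 68.5%, non-inferiority is concluded.

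Elsewhere the high-risk plan is mostly at two years. Section 9.3.2 states the power for a true 2-year EFS of 83%: "A study of 54 evaluable HR patients using a one-sided type I error rate of 0.05 and 14.5% NI margin will have 80% power". Section 9.1 relates the margin to the uncertainty in the AAML0631 24-month estimate. The high-risk futility rule in Section 9.3.3 compares the 2-year limit with 68.5%. The parallel standard-risk rule in Section 9.3.1 uses two years throughout. No AAML0631 comparator, margin or power is given for high-risk patients at three years.

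**The concern.** This sentence decides a primary objective. It compares a 3-year limit with a threshold built from a 24-month rate. EFS can only fall between years 2 and 3, so the mismatch works against non-inferiority, and the power in Section 9.3.2 does not describe the rule as written. With the analysis allowed two years after the last enrolment, the 3-year estimate would also rest partly on patients censored before 36 months.

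The plan gives no verdict if the 2-year lower limit clears 68.5% and the 3-year limit does not. Settling the time point once outcomes are known would be a data-driven choice on a primary endpoint.

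**Working it through.** **Inputs.** n = 54, one-sided alpha 0.05, margin 14.5 points, true 2-year EFS 83% (Section 9.3.2). Threshold 68.5% and 90% log-minus-log limits (9.3.1). High-risk accrual 11.5 per year, total accrual 5 years (9.2). High-risk cure model S(t) = 0.7973 + 0.2027·exp(−0.0976t), t in months (9.3.3).

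**Step 1: reproduce the stated power at two years.** With complete 2-year follow-up:

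- 11 events: S = 43/54 = 0.796, lower limit 68.8%, pass.
- 12 events: S = 42/54 = 0.778, lower limit 66.7%, fail.

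So the rule passes with at most 11 events.

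- Power: P(Bin(54, 0.17) ≤ 11) = 0.803.
- Alpha: P(Bin(54, 0.315) ≤ 11) = 0.049.

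The stated 80% is correct for 2-year EFS.

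**Step 2: EFS at three years under the protocol's curve.**

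- S(24) = 0.7973 + 0.2027·exp(−2.3424) = 0.8168.
- S(36) = 0.7973 + 0.2027·exp(−3.5136) = 0.8033.
- Exponent that sets 2-year EFS to 83%: ln 0.83 / ln 0.8168 = 0.921. Then 3-year EFS is 0.8033^0.921 = 81.7%.

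**Step 3: follow-up.** 54/11.5 = 4.7 years, or 56.3 months of accrual. With analysis 24 months after the last patient, those enrolled in the final 12 months have under 36 months of potential follow-up: 12/56.3 = 21% (12/60 = 20% for 5-year accrual).

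**Step 4: simulate both rules.** Kaplan-Meier with Greenwood log-minus-log 90% limits, 20,000 trials per case, uniform accrual over 56.3 or 60 months, no loss to follow-up. Entries are the probability that the lower limit exceeds 68.5%.

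| True curve | 2-year rule | 3-year rule, minimum follow-up 24 months | 3-year rule, minimum follow-up 36 months |
|---|---|---|---|
| 2-year 83%, 3-year 81.7% | 80.5–80.6% | 69.9–70.6% | 72.9–73.2% |
| Unscaled cure model: 81.7%, 80.3% | 71.6–72.4% | 60.4–60.5% | 62.8–62.9% |
| 2-year 68.5% (null), 3-year 66.4% | 4.8–5.0% | 2.2% | 2.2–2.3% |

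In the first row about 7 to 8 points are lost to year-3 events and a further 2 to 3 to censoring.

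**Step 5: dependence on year-3 events.** With 2-year EFS held at 83%, constant hazards before and after 24 months, and 60-month accrual, power of the 3-year rule is:

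| 3-year EFS | Power |
|---|---|
| 83% (no year-3 events) | 80% |
| 82% | 71% |
| 81% | 63% |
| 80% | 55% |

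**Step 6: the futility simulation.** Section 9.3.3 uses exponent 1.73 for the high-risk unfavourable scenario and labels it a 3-year EFS of 71%. But 0.8168^1.73 = 70.5% at 24 months and 0.8033^1.73 = 68.5% at 36 months. The exponents that would be needed are:

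- 68.5% at 24 months: ln 0.685 / ln 0.8168 = 1.87
- 68.5% at 36 months: ln 0.685 / ln 0.8033 = 1.728
- 71% at 24 months: ln 0.71 / ln 0.8168 = 1.692
- 71% at 36 months: ln 0.71 / ln 0.8033 = 1.564

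The value used fits 68.5% at 36 months best. It does not match its label, and it is not the 2-year null.

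**The case against.** The intended time point can be recovered. Comparator, hypotheses, estimator, follow-up, power and futility rule all point to two years, so a careful analyst would probably read the one stray phrase as a slip. It may be left over from the AIDA 0493 comparator, whose high-risk figure in Section 2.1 is at 3 years, though the documents do not say so. On that reading the sample size is right and the 80% is delivered. The error is also conservative: the 3-year rule rejects about 2% of the time at the 2-year null, and 4.3–4.5% if the 3-year rate itself is 68.5%, so it cannot push false non-inferiority claims above 5%. The power loss depends on year-3 events, and the censoring share is small and would shrink if the analysis came later than the stated minimum. On the futility curve, 70.5% at 24 months is close to the labelled 71%, so a swapped time label is nearly as good an explanation of the exponent.

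Most of this stands and limits the point: the power is not miscalculated, alpha is not inflated, and the loss applies to literal use of the rule. It does not settle the matter. A confirmatory rule should not need its time point inferred, a conservative error can still fail a truly non-inferior regimen, and three years also appears in the high-risk futility text. Whichever explanation of the exponent is right, that label and value still have to be reconciled.

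**Conclusion.** The concern holds. The decision rule for Primary Objective 2 contradicts its own hypotheses, threshold, power basis and follow-up. Used as written, its power is about 70% against the stated 80% at a true 2-year EFS of 83%, and about 60% against 72% under the unscaled cure model. These figures assume the protocol's curve shape (scaled by proportional hazards to reach 83%), 54 patients, uniform accrual over 56 to 60 months, analysis 24 months after the last patient, and no loss to follow-up. With 2-year EFS at 83%, the 3-year rule ranges from 80% power with no year-3 events to 55% if 3-year EFS is 80%. It should be corrected before any high-risk outcome analysis, because a later correction could not be separated from knowledge of the result.

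**What to change.** In Section 9.3.1, Primary Objective 2, make the decision sentence refer to the lower limit for 2-year EFS, and make the estimation sentence before it refer to high-risk patients. Three-year EFS can be reported descriptively if wanted. This is a wording change with no new patients, data or change in sample size, and it restores the stated 80% power.

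In the same amendment, reconcile the high-risk futility null in Section 9.3.3, so that its stated time point, EFS value and exponent agree with each other and with the 2-year threshold. If the exponent changes, the 58.4% stopping probability has to be re-simulated; that costs only computing time.

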9.3.2 Power Calculations

Primary Objective 1

A study of 96 evaluable SR patients using a one-sided type I error rate of 0.05 and 10% NI margin will have 80%, 91% and 97% power to reject the null hypothesis that the 2-year EFS is not non-inferior to 97% for a 2-year EFS of 95%, 96% and 97% respectively. Power calculations were performed using PASS 14.

Primary Objective 2

A study of 54 evaluable HR patients using a one-sided type I error rate of 0.05 and 14.5% NI margin will have 80% power to reject the null hypothesis that the 2-year EFS is not non-inferior to 83% for a 2-year EFS of 83%. Power calculations were performed using PASS 14.

Simulations of the impact of this futility monitoring plan on overall power were performed 500 times assuming that EFS for SR patients enrolled up to the time of the interim monitoring would follow a cure model, $S(t)$, consistent with a 2-year EFS of 97%. That is, $S(t) = [S_{AIDA}(t)]^{0.746}$, where $S_{0631}(t) = 0.906 + 0.094 \exp(-0.0238*t)$, t measured in months, is the cure model corresponding to the AAML0631 EFS results for SR patients. For those who have not experienced an EFS event by the time of analysis (including those who have not enrolled yet), EFS was simulated 500 times using the same cure model $S(t)$. The overall power accounting for stopping due to futility monitoring is 95%.

Futility monitoring – High Risk patients

The HR arm will be monitored for futility when approximately 50% of the expected number of EFS events have been observed (at least 6 of the 12 total events). The interim analysis is anticipated to occur after 80% of the patients are enrolled. We will calculate the conditional probability that the 90% log-minus-log transformed confidence limits for 2-year EFS exceeds 68.5%. For those who have not experienced an EFS event by the time of analysis, EFS time will be simulated under the alternative hypothesis using cure models consistent with 2-year EFS of 82%. If the conditional probability of rejecting the null hypothesis is less than 5%, the treatment arm will be identified for possible closure of accrual.

Simulations of the operating characteristics of this futility monitoring plan were performed 500 times assuming that EFS for HR patients enrolled up to the time of the interim monitoring would follow a cure model, $S(t)$, consistent with a 3-year EFS of 71%. That is, $S(t) = [S_{0631}(t)]^{1.73}$, where

$S_{0631}(t) = 0.7973 + 0.2027 \exp(-0.0976*t)$, t measured in months, is the cure model corresponding to the AAML0631 EFS results for HR patients. For those who have not experienced an EFS event by the time of analysis (including those who have not enrolled yet), EFS was simulated 500 times using a cure model, $S(t)$, consistent with a 2-year EFS of 82%. That is, $S(t) = [S_{0631}(t)]^1$. 58.4% of the time the conditional probability of rejecting the null hypothesis was less than 5%.

Simulations of the impact of this futility monitoring plan on overall power were performed 500 times assuming that EFS for HR patients enrolled up to the time of the interim monitoring would follow a cure model, $S(t)$, consistent with a 2-year EFS of 82%. That is, $S(t) = [S_{0631}(t)]^1$, where

$S_{0631}(t) = 0.7973 + 0.2027 \exp(-0.0976*t)$, t measured in months, is the cure model corresponding to the AIDA 0493 EFS results for HR patients. For those who have not experienced an EFS event by the time of analysis (including those who have not enrolled yet), EFS was simulated 500 times using this cure model $S(t)$. The overall power accounting for stopping due to futility monitoring is 78%.

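### The 78% overall power for the high risk stratum is above the 72.2% that its printed curve allows before any futility loss, and the high risk futility null is inconsistent in label, exponent and time point

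*Combined protocol and SAP*

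**What the plan says.** Section 9.3.2 gives 54 evaluable HR patients 80% power, at one-sided 5% with a 14.5-point margin, when the true 2-year EFS is 83%. Section 9.3.1 (Primary Objective 2) sets 2-year hypotheses and a 2-year Kaplan-Meier estimate with 90% log-minus-log limits. Its decision sentence, however, begins "If the lower confidence limit for the 3-year EFS exceeds" and then gives the bound of 68.5%. The final analysis waits at least 2 years after the last HR enrolment.

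Section 9.3.3 (Futility monitoring – High Risk patients) has three parts that matter here:

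- **Rule.** The look uses the conditional probability that the "transformed confidence limits for 2-year EFS exceeds 68.5" percent. If this is below 5%, "the treatment arm will be identified for possible closure of accrual".
- **Futility null.** Patients enrolled before the look follow a curve described as "consistent with a 3-year EFS of 71" percent, generated as S0631(t) to the power 1.73. The base curve 0.7973 + 0.2027 exp(−0.0976t) "is the cure model corresponding to the AAML0631 EFS results for HR patients". The rule stops 58.4% of 500 simulated trials.
- **Overall power.** Patients follow the same base curve with exponent 1, described as "consistent with a 2-year EFS of 82" percent. Here the identical formula "is the cure model corresponding to the AIDA 0493 EFS results for HR patients". The result is: "The overall power accounting for stopping due to futility monitoring is 78" percent.

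**The concern.** Stopping for futility can only remove successes, so overall power cannot exceed the power of the final test alone at the same truth. The plan has 80% at 83%. Moving the truth down to about 82% and adding a stopping rule should cost more than two points, because power falls steeply in this range with 54 patients. The 78% therefore looked too high.

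It is the only HR power figure that accounts for futility. If the printed curve is the truth, the chance of failing to show non-inferiority is about 28% rather than the 22% a reader would infer.

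The 58.4% raises a separate problem. Its meaning depends on where the null sits relative to the 68.5% bound, and the label, the exponent and the 2-year rule point to different places.

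**Working it through.** **Inputs.** n = 54 (9.3.2); bound 68.5% and 90% log-minus-log limits (9.3.1, 9.3.3); curve S(t) = 0.7973 + 0.2027 exp(−0.0976t) (9.3.3); 500 simulations (9.3.3). Assumption: no loss to follow-up before 24 months. Since the final analysis comes at least 2 years after the last enrolment, the 24-month Kaplan-Meier estimate is then a simple proportion of 54.

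**Pass mark.** With x events and p = 1 − x/54, the lower limit is p^exp{1.645 √[(1−p)/(54p)] / |ln p|}.

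- x = 11: p = 0.7963, limit 0.6877, pass.
- x = 12: p = 0.7778, limit 0.6673, fail.

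Power is therefore P(Bin(54, 1 − EFS) ≤ 11).

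**Reproducing the plan's own figures.** At EFS 83% this gives 80.3% (plan: 80%). For standard risk, with n = 96 and bound 87%, the rule passes with at most 6 events. Power is 79.5%, 91.0% and 97.4% at 95%, 96% and 97% (plan: 80%, 91%, 97%). The standard risk overall power of 95% lies below its no-futility value of 97.1% at the printed curve (exponent 0.746, EFS 96.9%), as it must.

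**HR overall power.** S(24) = 0.7973 + 0.2027 exp(−2.3424) = 0.8168. Rounding of the printed coefficients moves this only between 0.8167 and 0.8168.

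| True EFS at the test point | Power, no futility |
|---|---|
| 81.7% (printed curve, 24 months) | 72.2% |
| 82% exactly | 74.3% |
| 83% (design value in 9.3.2) | 80.3% |
| 80.3% (printed curve, 36 months) | 63.0% |

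A power of 78% needs a true 2-year EFS of 82.6%.

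**Simulation error.** At 72.2%, the standard error for 500 runs is √(0.7224 × 0.2776/500) = 2.0 points. The gap of 5.8 points is 2.9 standard errors, and an estimate that rounds to 78% or more (at least 388 of 500) has probability 0.4%. At 74.3% the gap is 3.7 points, 1.9 standard errors, with probability 5%.

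**Cost of the futility look.** I simulated the rule 20,000 times per setting. The assumptions were uniform accrual at 0.90 or 0.96 HR patients per month (54 in 5 years; 11.5 per year) and a look at the 44th enrolment, with and without requiring 6 events. At 81.7% the look stops 5.0% to 5.4% of trials and costs 0.07 to 0.15 points of power. Overall power stays at about 72%. Loss to follow-up of 2% or 5% per year, without futility, lowers power to about 67% or 65%.

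**Futility null.** S(36) = 0.8033.

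| Quantity | 24 months | 36 months |
|---|---|---|
| EFS with exponent 1.73 | 70.5% | 68.5% |
| Exponent needed for 71% | 1.69 | 1.56 |
| Exponent needed for 68.5% | 1.87 | 1.73 |

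Exponent 1.73 therefore puts the null on the 68.5% bound at 3 years, not at the labelled 71%. At the 2-year test point it lies 2 points above the bound. The standard risk labels do match their exponents at 2 years: 3.41 gives 86.7% (labelled 87%) and 0.746 gives 96.9% (labelled 97%).

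**The case against.** - **The run may have used another curve.** If the simulation was done at 83%, the expected result is about 80%. With a standard error of √(0.8032 × 0.1968/500) = 1.8 points, 78% would be unremarkable (2.3/1.8 = 1.3 standard errors). The power would then be roughly right and the printed curve wrong. This stands as a possible cause; the document cannot settle it. Either way, the figure and the curve printed beside it do not belong together.
- **The gap depends on a fraction of a point of EFS.** At exactly 82% it is borderline. That is correct, but the plan defines the simulation by its formula, which gives 81.7%, and 82% is only the rounded label.
- **Another calculation might give 78%.** A log-log normal approximation using the null standard error gives 75.9% at the printed curve and 77.6% at 82%, but 82.4% at 83%, where the plan says 80%. A Wald approximation gives 80.5% at the curve but 88.3% at 83%. Neither describes a simulation of the stated Kaplan-Meier rule.
- **The exponent is coherent with a 3-year test.** It is: 1.73 gives the 68.5% bound at 36 months. The 71% resembles the AIDA 0493 value of 71.1% at 3 years in Section 2.1 and may be left over from the former comparator. But the hypotheses, power and futility rule are 2-year, so the conflict remains. The 58.4% itself is not shown to be wrong. Depending on accrual and interim timing, simulation gives stop rates of about 48% to 54% for exponent 1.73 and about 60% to 65% for 1.87, and 58.4% lies between.
- **The practical effect is small.** This is conceded. The look only flags the arm for possible closure, and the 80% at 83% is almost untouched by futility.

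**Conclusion.** The concern holds. As printed, the HR overall power is overstated: 72.2% is the ceiling under the stated curve, sample size and decision rule, against 78% reported. Reading the test at 3 years widens the gap. This rests on complete 2-year follow-up, which favours the plan, and on the printed curve being the one simulated. Confidence is high that 78% does not follow from the printed inputs. The size of the error depends on whether the run used 81.7%, exactly 82%, or something else.

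The HR futility null is internally inconsistent, so a reader cannot be sure which truth the 58.4% describes. Two wording conflicts are also plain on the page: the 3-year limit in the HR decision sentence, and the attribution of one formula to both AAML0631 and AIDA 0493. The 3-year wording matters most of these, because it sits in a primary decision rule.

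**What to change.** 1. State which curve was used for the HR overall-power simulation, rerun it, and restate the result: about 72% at the printed curve, about 74% if the truth is exactly 82%, or about 80% if reported at the design value of 83%.
2. Give the HR futility null one time point, one label and one exponent. Placing it at the 2-year bound of 68.5% (exponent 1.87) would match the standard risk approach and the 2-year criterion. Then confirm or restate the 58.4%, giving the accrual pattern and interim timing used.
3. In Section 9.3.1, Primary Objective 2, bring the 3-year wording of the decision sentence into line with the 2-year hypotheses.
4. In Section 9.3.3, correct the AIDA 0493 attribution in the HR overall-power paragraph and the similar AIDA subscript in the standard risk overall-power paragraph.

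The cost is a short simulation rerun and text edits. The stated power becomes less favourable unless it is reported at 83%. Sample size, margin and the 2-year final test do not change.
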